2. INTRODUCTION AND BACKGROUND

2.1. STUDY RATIONALE

Severe acute respiratory syndrome coronavirus 2 (SARS-CoV-2) is a novel human pathogen that emerged at the end of 2019 and rapidly spread worldwide caused a global pandemic. SARS-CoV-2, an enveloped, positive-sense, single-stranded RNA beta-coronavirus of the family Coronaviridae that causes COVID-19. Patients with COVID-19 have had mild to severe respiratory illness with symptoms of fever, cough, and shortness of breath along with non-specific symptoms including myalgia and fatigue. Many infected people are asymptomatic or experience mild symptoms and recover without medical intervention. Some patients are more likely to develop a severe respiratory illness including pneumonia, severe acute respiratory syndrome, multi-organ failure, and death.

Along with the development of new antiviral drugs, repurposing of existing drugs for COVID-19 treatment has also accelerated. A number of clinical studies have been conducted to test the efficacy of FDA-approved drugs, re-purposed for COVID-19 (lopinavir, chloroquine, favipiravir, and remdesivir (RDV). At present, the main antiviral strategies currently employed against SARS-CoV-2 can be divided into two types: strategies directly targeting the virus and strategies indirectly targeting the virus via host modulation. Despite some drugs demonstrated good efficacy, there are number of patients not responsive to available anti-COVID-19 therapy. There is no specific antiviral treatment recommended for COVID-19 by Centers for Disease Control and Prevention (CDC). People with COVID-19 should receive supportive care to help relieve symptoms. For severe cases, treatment should include care to support vital organ functions. Clinical management includes symptomatic and supportive care, such as supplemental oxygen, mechanical ventilation, and extracorporeal membrane oxygenation (ECMO) when indicated. Therefore, development of an effective antiviral drug for COVID-19 is a global health priority and discovery of novel cellular targets for SARS-Cov2 coronavirus has led to novel putative clinical strategies which merit going into clinical research in COVID-19.

2.2. BACKGROUND

Silmitasertib is a first-in-class small molecule drug that targets Casein Kinase 2 (CK2). Protein kinase CK2 phosphorylates key proteins required to trigger mechanisms vital for viral replication and also is involved in development of host anti-viral immune response. To counter host immune response and create more favorable environment for infection and viral multiplication, viruses have developed an arsenal of strategies. SARS-CoV-2 viral proteins interacting with many human host proteins affect multiple innate immune pathways. One of these key proteins dysregulated by SARS-CoV-2 is the protein kinase CK2. Previous study showed that CK2 is involved in SARS-COV-2 nucleocapsid (N-protein) interactome (virus-host protein interactions). SARS-COV-2 upregulates CK2 to support viral replication, avoid innate immune response and spread virus to nearby cells.

CONFIDENTIAL Page 17 of 66

Over activation of CK2 indirectly contribute to successful viral replication and development of cytokine storm.

Researchers noted that the disruption of CK2, promotes the formation of Stress Granules (SGs), resulting in host cell translational arrest and significant limitation of the resources in cells required for viral replication [1]. Besides, SARS-CoV2 uses over activated CK2 in the infected cells to stimulate production of filopodia, as CK2 can promote actin polymerization and regulates cytoskeleton organization. Filopodia with assembled viral particles can invade and transfer the disease in the nearby healthy cells. Induction of virus-containing filopodia are important for SARS-CoV-2 egress and cell-to-cell spread within epithelial monolayers. CK2 is also an important protein for Retinoic acid-inducible gene I (RIG-I) helicase activity regulation. RIG-I is an intracellular RNA virus sensor that mediates a signaling pathway that triggers alpha/beta interferon (IFN- α/β) immune defenses. CK2 phosphorylates a RIG-I repressor domain to inactivate RIG-I in the resting uninfected state. SARs-Cov-2-induced overexpression of CK2 suppresses RIG-I-mediated signaling, while pharmacological inhibition of CK2 enhances expression of IFN- β and suppresses virus proliferation. CK2 signaling appears to be an important pathway hijacked by SARS-CoV-2.

2.3. SILMITASERTIB (CX-4945)

Silmitasertib (CX-4945) is a first-in-class potent and highly selective small molecule inhibitor of CK2 that interacts competitively with the ATP-binding site of CK2 subunit alpha, leading towards the inhibition of several downstream signaling pathways. CK2 is involved in regulation of signaling pathways (Sonic Hedgehog (SHH), IL-6/STAT3, mTOR signaling pathways) through protein phosphorylation and also plays a multifunctional role in signal transduction, transcriptional control, apoptosis and inflammation. Overexpression of CK2 was observed in diseases with high proliferative activities, inflammatory reaction and dysregulated immune response (viral infections, auto-immune inflammations, cancer).

The biological activity of CX-4945 has been evaluated in both in vitro and in vivo studies:

- CX-4945 demonstrated strong anti-viral efficacy in human cells infected by SARS-CoV-2 (pre-clinical in vitro study). [2]
 (https://www.biorxiv.org/content/10.1101/2020.04.21.054387v1)
- CX-4945 significantly reduced replication of human papillomavirus in vivo. [3]
- In several pre-clinical and clinical trials in the diseases driven by pro-inflammatory cytokines CX-4945 demonstrated anability to significantly reduce plasma level of interleukins (IL-6, IL-8, IL-17) in vitro and in vivo (inflammatory breast cancer, Alzheimer's disease, autoimmune encephalomyelitis). [4]
- CK2 inhibitor down-regulated replication, budding and release of influenza virus in preclinical studies. [5]
- CK2 inhibitor reduced phosphorylation dependent ICP27 protein export, which is necessary for its ability to export herpes simplex viral RNAs. [6]
- CX-4945 also demonstrated anti-tumor activity in a variety of primary human xenografts and tumor cell line xenograft models and in clinical trials.

Silmitasertib (CX-4945) is currently under development in several oncology programs in adults and in children with recurrent/advanced or metastatic cancer. CX-4945 is being used as an antitumor agent that inhibits the Sonic Hedgehog signaling pathway (basal cell carcinoma, medulloblastoma) and/or DNA repair in tumor cells damaged by chemotherapy (cholangiocarcinoma) through inhibition of CK2. Three phase I clinical trials of CX-4945 in cancer patients have been completed to date (solid tumors, multiple myeloma), and there is one ongoing phase I study (BCC) and two ongoing phase II studies (CCA, Medulloblastoma).

The purpose of this open-label, 2 arm parallel-group, randomized, controlled interventional prospective exploratory, Investigator-Initiated Trial (IIT) in 40 patients is to evaluate safety and tolerability of Silmitasertib (CX-4945) 1000 mg BID dose. Secondary objectives will be used to make an initial assessment of the potential for clinical benefit. The drug supplier, Senhwa

CONFIDENTIAL Page 20 of 66

Biosciences, is taking steps toward a subsequent randomized, double-blind, placebo-controlled study in a large number of subjects (NIH-sponsored ACTIV study).

2.4. RISK/BENEFIT ASSESSMENT

Silmitasertib is a generally well-tolerated medication. Most adverse events reported were mild to moderate in severity. The most common toxicities associated with CX-4945 were gastrointestinal disorders, manageable with drug discontinuation or use of anti-diarrheal medication. Based on the currently available data, the identified or potential risks of the product do not outweigh its identified or potential benefits.

CONFIDENTIAL Page 21 of 66

3. OBJECTIVES AND ENDPOINTS

Primary Objective	Primary Endpoint
To assess safety and tolerability of CX-4945 administered orally twice daily to patients with severe COVID-19	• Adverse Events experienced by patients from randomization to Day 60 (including vital signs, physical findings, clinical laboratory, and ECG results) as characterized by type, frequency, severity (as graded by Common Terminology Criteria for Adverse Events (CTCAE version 5.0), timing, seriousness, and relationship to study therapy.
Secondary Objectives	Secondary Endpoints
• To compare time to clinical recovery in the CX-4945 treatment group evaluated from randomization through Day 28 as compared to the control arm.	• Number of days from randomization to discharge, or alleviation of cough (defined as mild or absent in a patient reported scale of 0=absent, 1=mild, 2=moderate, and 3=severe). Improvement must be sustained for at least 48 hours.
	• Number of days from randomization to normalization of fever (defined as <36.6°C from axillary site, or < 37.2°C from oral site or < 37.8°C from rectal or tympanic site), normalization of respiratory rate (< 24 bpm while breathing room air), resolution of hypoxia (defined as SpO2 ≥ 93% in room air or P/F ≥ 300 mmHg). All these improvements must be sustained for at least 48 hours.
	 Number of days from randomization to the first day on which the subject satisfies one of the following three categories from the ordinal NIAID 8-point Clinical Progression Outcomes scale collected daily from randomization through Day 28:
	Hospitalized, not requiring supplemental oxygen - no longer requires ongoing medical care;
	 Not hospitalized, limitation on activities and/or requiring home oxygen;
	Not hospitalized, no limitations on activities.
To compare changes in clinical status of patients enrolled to CX-4945 treatment arm as	Difference in percentage of subjects with clinical recovery compared at Day 14 and Day 28. Clinical recovery is defined as:

CONFIDENTIAL Page 22 of 66

s. ty	ite, or < 37.2°C from oral site or < 37.8°C from rectal or ympanic site), normalization of respiratory rate (< 24 bpm
a	while breathing room air), resolution of hypoxia (defined as $SpO2 \ge 93\%$ in room air or $P/F \ge 300$ mmHg). All these mprovements must be sustained for at least 48 hours.
Day	centage of participants at each clinical status at Day 14 and 28 assessed by using the ordinal NIAID 8- point Clinical gression Outcomes scale:
1) L	Death;
	Hospitalized, on invasive mechanical ventilation or acorporeal membrane oxygenation (ECMO);
· · · · · · · · · · · · · · · · · · ·	Hospitalized, on non-invasive ventilation or high flow gen devices;
4) H	Hospitalized, requiring supplemental oxygen;
	Hospitalized, not requiring supplemental oxygen - requiring oing medical care (COVID-19 related or otherwise);
· ·	Hospitalized, not requiring supplemental oxygen - no longer uires ongoing medical care;
	Not hospitalized, limitation on activities and/or requiring ne oxygen;
8) N	ot hospitalized, no limitations on activities
evidence of anti-viral activity of CX-4945 as compared to the Day	Gerence in proportions of patients with conversion of tive RT-PCR to negative RT-PCR as assessed at Day 1, 8, Day 14 and Day 28
	inges in chest imaging from Screening (Day 0)to Day 5 or 14 (if applicable) as defined by:
0]	Number of quadrants/ pulmonary lobes affected

CONFIDENTIAL Page 23 of 66

	 Change in number and/or size of COVID-19 pulmonary lesions (ground-glass opacity, consolidation, mix pattern) assessed by chest CT/X-ray
To evaluate the Clinical Benefit of Silmitasertib (CX-4945) relative to the control arm in patients with Severe COVID-19.	 Days of hospitalization from randomization through Day 28. Days of supplemental oxygen (if applicable) from randomization through Day 28. All-cause mortality status: the number of deaths occurred in each treatment group from randomization through Day 60. Days of non-invasive ventilation/high flow oxygen (if applicable) from randomization through Day 28. Days of invasive mechanical ventilation/ECMO (if applicable) from randomization through Day 28. Number of patients returned to room air after randomization through Day 14 or Day 28. Change in pulse oxygen saturation (SpO2) from randomization to Day 4, 8, 11, 14 and 28. Number of documented venous thromboembolism (VTE), arterial thrombosis (stroke, myocardial infarction, other) and microthrombosis events from randomization through Day 28. Changes in EQ-D5-5L (used as an indicator of symptom improvement) from randomization to Day 8, 14 and 28.
To evaluate changes in inflammatory markers	 Changes in plasma IL-6 level from randomization to Day 4, 8, 11, and 14 Changes in CRP, LDH, CPK, ferritin, D-dimer from randomization to Day 4, 8, 11, and 14

CONFIDENTIAL Page 24 of 66

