5.1.1. Inclusion Criteria

Patients must meet all of the following inclusion criteria to be eligible for enrollment in the study:

- 1. Male or non-pregnant female adult ≥ 18 years of age
- 2. Diagnosed or confirmation of COVID-19 infection by standard RT-PCR assay or equivalent testing within 7 days prior to randomization (Day1).
- 3. Hospitalized patient with severe illness caused by SARS-CoV-2 (**Note:** Prior or current use of remdesivir or dexamethasone (SOC) are allowed under the investigator's discretion. Concomitant treatment with other investigational antiviral drugs or immunomodulators are not permitted from Day1 through Day 28)
 - Symptoms of severe systemic illness/infection with COVID-19:
 - At least 1 of the following: fever, cough, sore throat, malaise, headache, muscle pain, shortness of breath at rest or with exertion, confusion, or symptoms of severe lower respiratory infection including dyspnea at rest or respiratory distress

AND

- Clinical signs indicative of severe systemic illness/infection with COVID-19
 - At least 1 of the following: $RR \ge 30$, $HR \ge 125$, SaO2 < 93% on room air or requires $\ge 2L$ oxygen in order to normalize SaO2.
- 4. Patient (or legally authorized representative) provides written informed consent prior to initiation of any study procedures.
- 5. Adequate hematopoietic capacity, as defined by the following:
 - a. Hemoglobin \geq 9.0 g/dL and not transfusion dependent
 - b. Platelets $> 100,000/\text{mm}^3$
 - c. Absolute neutrophil count $\geq 1500 \text{ cells/mm}^3$

CONFIDENTIAL Page 27 of 66

- 6. Adequate hepatic function, as defined by the following:
 - a. AST and ALT ≤ 2.5 times upper limit of normal (ULN)
 - b. Total bilirubin $\leq 1.5 \text{ x ULN}$
 - c. Albumin $\geq 2.5 \text{ g/dL}$
- 7. Absence of any active or recurring clinically significant hepatic disease and adequate renal function, as defined by the following:
 - a. Renal: calculated creatinine clearance >45 mL/min for patients with abnormal, increased creatinine levels (Cockcroft-Gault formula).
- 8. Ability to take oral medication and be willing to adhere to drug administration and premedication requirements (see **Section 6.3**) throughout study duration.

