6.1.5. Silmitasertib (CX-4945) Dose Modifications

The most common drug related adverse events reported for CX-4945 are predominantly gastrointestinal disorders, including nausea, vomiting and diarrhea. The dose interruption, reduction, and permanent discontinuation for any toxicity are described below. Dose modification instructions provided bellow do not substitute for investigators' medical judgement. Investigators should always manage their patients according to their medical judgement based on the particular clinical circumstances.

Table 3. Silmitasertib (CX-4945) Dose Modification and Management for potential toxicities (attributable to Silmitasertib)

CTCAE 5.0 Grade (attributable to Silmitasertib)	Treatment Modifications
Grade 1	Treat on time. dose reduction is not required
Grade 2	Hold until≤ Grade 1, resume at same dose
Grade 3	Hold until< Grade 2, resume at dose reduced by 1 level (200 mg)
Grade 4	Hold until Grade 2, resume at dose reduced by 1 level (200 mg).
	Permanent discontinuation can be considered by at the
	Investigator's discretion

• **Dose Reduction:** If a dose-response relationship for toxicity is observed, a reduced dose can be given to the subject. Dose adjustments will be allowed based on the toxicity, efficacy evaluation, and clinical judgment by physician.

CONFIDENTIAL Page 31 of 66

- **Dose Interruption:** Refer to Table 3 above. Recovery to acceptable levels must occur to allow Silmitasertib (CX-4945) continuation.
- **Dose Discontinuation:** Treatment with CX-4945 can be discontinued prematurely due to the following reasons:
 - Disease Progression
 - o Respiratory failure requiring invasive mechanical ventilation,
 - Shock (defined by SBP < 90 mm Hg, or Diastolic BP < 60 mm Hg), or
 - Multiple organ dysfunction/failure
 - Intolerable toxicity most probably attributable to CX-4945.
 - Pregnancy
 - o Significant study therapy non-compliance
 - o If any clinical adverse event (AE), laboratory abnormality, or other medical condition or situation occurs such that continued treatment under the protocol would not be in the best interest of the participant
 - Withdrawal of consent from study treatment or participation

Discontinuation from the study drug does not mean the withdrawal from the study assessments. Subjects who discontinued therapy should remain in the study and continue follow-up for key outcomes. The only reasons for study withdrawal are withdrawal of consent from study participation and loss to follow-up.

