8.2.1.3. Vital Signs and Physical Examination

Patients will have a full physical examination to include an examination of all major body systems, height (at screening only), weight, blood pressure and pulse rate, which may be performed by a physician, registered nurse or other qualified health care provider, as acceptable according to local regulation. A symptom-directed physical examination should be limited to systems of primary relevance (i.e., cardiovascular, respiratory, and systems associated with symptoms). Changes from baseline abnormalities should be recorded at each subsequent physical examination. New or worsened abnormalities should be recorded as an adverse event.

Pulse oximetry should be collected prior to collection of the blood pressure, pulse rate, and temperature. Oxygen levels should be evaluated on the finger in accordance with the site standard procedures. All abnormalities will be evaluated by the study physician.

Blood pressure, heart rate, respiration rate, and temperature should be recorded after approximately 5 minutes rest. An abbreviated physical exam is an assessment for emergent toxicities or changes from prior visits and a symptom directed exam conducted by a physician, trained physician's assistant or nurse practitioner, as acceptable according to local regulation.

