8.3.1. Definitions of Adverse Event (AE)

An adverse event (AE) is defined as any unfavorable or unintended sign, symptom, or disease that occurs or is reported by the patient to have occurred, or a worsening of a pre-existing condition. An adverse event may or may not be related to the study treatment.

AEs will be elicited through direct questioning and subject reports. Any abnormality in physical examination findings or laboratory results that the investigator believes is clinically significant (CS) to the research subject and that occurred after initiation of the first study treatment will be reported as AEs. Abnormal findings that are NOT clinically significant should not be recorded as an AE.

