8.3.2. Definition of Serious Adverse Events

CONFIDENTIAL Page 43 of 66

A SAE is defined as any AE that:

- Results in death
- Is life threatening (the subject is at immediate risk of dying from the adverse experience)
- Requires subject hospitalization or prolongs existing hospitalization
- Results in persistent or significant disability/incapacity
- Is a congenital anomaly/birth defect
- Important medical events that may not result in death, be life-threatening, or require hospitalization may be considered a serious adverse effect when, based upon appropriate medical judgment, they may jeopardize the subject or subject and may require medical or surgical intervention to prevent one of the outcomes listed in this definition.

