9.8.4.3. Safety Summaries

Adverse Events

Adverse events will be coded using the most recent version of Medical Dictionary for Regulatory Activities (MedDRA). Treatment Emergent AE's (TEAE) are defined as events with an onset on or after the first treatment. TEAEs will be summarized by treatment group, System Organ Class, and preferred term. The following TEAE summaries will be provided:

- Overall (i.e., regardless of severity or relationship to treatment);
- By intensity (mild, moderate, severe, life threatening or death);
- By causality (definitely, probably, possibly, remotely or unrelated);
- By impact on study treatment (dose increased, dose not changed, dose rate reduced, dose reduced, drug interrupted, drug withdrawn, not applicable, or unknown).

In addition, separate summaries of serious adverse events, and adverse events resulting in discontinuation of study treatment will be presented.

Clinical Laboratory Data

All laboratory values will be listed. Laboratory measurements will also be summarized and presented by treatment group and time point.

CONFIDENTIAL Page 52 of 66

ECG

All ECG values will be listed. ECG measurements will also be summarized and presented by treatment group and time point.

Vital Signs

All vital sign findings will be listed and/or summarized.

Physical Examination

All physical examination findings will be listed and/or summarized.

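### Worsening COVID-19 is pooled with other events in the headline adverse-event summaries, which dilutes a CX-4945 toxicity difference and can offset it if the drug also reduces progression

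*Combined protocol and SAP*

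**What the plan says.** The primary endpoint in Section 3 is "Adverse Events experienced by patients from randomization to Day 60 (including vital signs, physical findings, clinical laboratory, and ECG results"), described by type, frequency, severity, timing, seriousness and relationship to study therapy.

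Section 8.3.1 defines an adverse event broadly, ending "or a worsening of a pre-existing condition. An adverse event may or may not be related to the study treatment". Section 8.2.1.3 adds, for physical examinations, "New or worsened abnormalities should be recorded as an adverse event". Section 8.3.2 makes an adverse event serious if, among other criteria, it is fatal or life-threatening, or it "Requires subject hospitalization or prolongs existing hospitalization". Section 5.1.1 requires a "Hospitalized patient with severe illness caused by SARS-CoV-2", so the disease is pre-existing at randomization. No section exempts COVID-19 progression from adverse-event reporting.

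Section 6.1.5 does draw a line between disease and drug. Among the reasons for stopping CX-4945 it lists disease progression ("Respiratory failure requiring invasive mechanical ventilation", shock, multiple organ dysfunction) apart from intolerable toxicity attributed to CX-4945.

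Section 9.8.4.3 plans treatment-emergent events by arm, system organ class and preferred term: overall, by intensity, by causality and by impact on treatment. In addition, "separate summaries of serious adverse events, and adverse events resulting in discontinuation of study treatment will be presented". None of these summaries is split into disease progression and other events. Sections 9 and 9.8 leave detailed methods to a separate SAP whose text is not in the documents.

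**The concern.** The primary question is whether CX-4945 adds harm. In these inpatients, COVID-19 respiratory failure and COVID-19 death are adverse events, usually serious ones, and ventilation, ordinal status and mortality are also secondary outcomes in Section 3. An any-serious-event rate by arm therefore mixes drug harm with the disease outcome that the drug is meant to improve.

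The planned breakdowns do not supply the missing figure, which is the number of patients per arm with any severe or serious event other than COVID-19 progression:

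- Preferred-term rows show terms one at a time, so single-patient toxicities scattered over several terms are easy to miss with 20 per arm.
- Causality (Section 8.3.3.2) is judged by the investigator in an open-label trial, in relation to a drug that Arm B never receives. Several of its criteria also turn on whether the patient's own clinical state could explain the event.

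At stake is a reading of similar serious-event rates that reflects harm and benefit offsetting each other. Section 2.3 says a larger randomized trial is being prepared, and such a reading would carry into it.

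**Working it through.** The plan gives no figure to reproduce. Section 9.3 sets 40 patients (20 per arm) by clinical judgment, and the documents state no event rates. What follows is an illustration under assumed rates.

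**Inputs.** From Section 9.3: n = 20 per arm. Assumed: progression pB in Arm B and pA in Arm A, and serious toxicity t in Arm A only. Progression and toxicity are taken as independent, and at first there are no other serious events.

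**Formulas.**

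- Any-serious-event rate: Arm B = pB; Arm A = 1 − (1 − pA)(1 − t).
- P(A ≤ B), the chance that Arm A shows no more affected patients than Arm B, is the sum over a ≤ b of Bin(a; 20, rate A) × Bin(b; 20, rate B).
- Toxicity rate at which the expected pooled rates are equal: t* = 1 − (1 − pB)/(1 − pA).

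**Pooled rate, t = 15%, pB = 35%.**

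| Effect on progression | Arm A rate | Arm B rate | Expected patients A v B | P(A ≤ B) |
|---|---|---|---|---|
| Benefit, pA = 20% | 1 − 0.80 × 0.85 = 32% | 35% | 6.4 v 7.0 | 64% |
| None, pA = 35% | 1 − 0.65 × 0.85 = 44.75% | 35% | 8.95 v 7.0 | 32% |
| Harm, pA = 50% | 1 − 0.50 × 0.85 = 57.5% | 35% | 11.5 v 7.0 | 10% |

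The middle row is dilution: a true excess of 15 points shows as 9.75. Only the first row offsets the toxicity. In the last row pooling makes the excess larger.

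**A higher toxicity rate.** With t = 25% and the same benefit, Arm A is 1 − 0.80 × 0.75 = 40% v 35%. The excess shrinks but keeps its sign.

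**How much toxicity a benefit can mask.** For 35% falling to 20%, t* = 1 − 0.65/0.80 = 18.75%. Over a wider range, with RR the relative risk of progression (pA = pB × RR):

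| pB | t* at RR 0.75 | t* at RR 0.5 |
|---|---|---|
| 20% | 5.9% | 11.1% |
| 30% | 9.7% | 17.6% |
| 40% | 14.3% | 25.0% |
| 50% | 20.0% | 33.3% |

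**After the split.** The non-progression row depends on q, the assumed rate of other serious events in both arms: Arm A = 1 − (1 − q)(1 − t), Arm B = q. With t = 15%:

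- q = 0: 3 v 0 patients expected; chance of none in Arm A = 0.85^20 = 3.9%.
- q = 10%: 1 − 0.90 × 0.85 = 23.5% v 10%; P(A ≤ B) = 17%.
- q = 20%: 1 − 0.80 × 0.85 = 32% v 20%; P(A ≤ B) = 24%.

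Each compares with 64% for the pooled row under the same toxicity and the benefit on progression.

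**The case against.** The strongest reply is that the primary endpoint is not one pooled rate. It is a multi-part description, and the known toxicity is gastrointestinal (Sections 2.4 and 6.1.5), which falls in a different organ class from respiratory failure. All subject data are listed (Section 9.7), the monitoring committee reviews event listings (Section 9.9), and deaths and ventilation days are reported by arm beside the safety tables. The causality scale names disease among the causes of an unrelated event. This stands as mitigation, and it is why the point is confined to the overall, intensity and serious summaries. It still gives no by-arm patient count of non-progression events. The term list is not free of open-label judgment either, since the same investigators report the events, but it applies one rule to both arms.

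Four stronger readings are tempting, and the documents do not support them:

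- **A loss of power.** With 25% toxicity, a two-sided 5% Fisher test has 59% power with progression excluded, 10% with a 35% progression background in both arms, and 3% if the drug also cuts progression to 20%. Section 9.8.4 plans only descriptive safety summaries, so no planned test loses this power. The 59% also assumes no other serious events in Arm B; with 10% or 20% of them in both arms it is about 30% or 19%.
- **That toxicity will be cancelled whatever the rates.** Offsetting needs a real benefit on progression, and whether the sign reverses depends on the rates.
- **That every prolonged stay is an adverse event.** Prolongation is a criterion that makes an adverse event serious; it is not itself an event. Section 8.3.1 also limits examination and laboratory findings to clinically significant ones.
- **That no split is planned anywhere.** The separate SAP could contain one.

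**Conclusion.** The concern holds in a limited form. The definitions and Section 9.8.4.3 put COVID-19 worsening into the headline adverse-event rates, although Section 6.1.5 treats progression and toxicity as different things. This dilutes a toxicity difference and, if CX-4945 reduces progression, can offset it. In the illustration, 15% serious toxicity appears as 32% v 35%. Over the range tabulated, expected rates become equal at toxicity of roughly 6% to 33%. These sizes rest on assumed rates, on independence of disease and drug events, and on no other serious events in the pooled rate. The inclusion of COVID-19 worsening is itself inferred from the general definitions and the absence of an exemption.

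No planned test is invalidated, and the split does not make 20 per arm precise: at a 30% rate the 95% half-width of a difference is 1.96 × √(2 × 0.3 × 0.7/20) = 28 points. The change is still worth making, because it bears on the primary objective and costs little.

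**What to change.** Keep the all-event tables as primary, so that harm appearing as worse COVID-19 stays visible. In Section 9.8.4.3, or in the SAP, add by-arm counts of patients (n/N) with any adverse event, Grade 3 or higher, serious and fatal events, each split into COVID-19 progression and all other events. Give the risk difference with an exact 95% confidence interval, labelled as a descriptive measure of precision.

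- Define progression by a MedDRA preferred-term list fixed before any by-arm output and applied alike in both arms.
- Limit the list to terms specific to COVID-19 respiratory progression. Leave shock and multiple organ dysfunction in the other-event rows, or show the table both ways, because they could also reflect toxicity. The protocol itself flags vomiting, diarrhea and electrolyte disturbance with arrhythmia risk (Sections 6.1.5 and 6.3.3).
- Show events leading to CX-4945 discontinuation for Arm A only, since Arm B has no study drug to stop.

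The cost is one term list and one extra set of rows, with no change to data collection, sample size or patient management. The downside is small: a toxic event coded to a listed term drops out of the other-event rows, which is a further reason to keep the all-event tables.
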